4.9. Drug accountability

The arrival of the study medication at the hospital pharmacy and the delivery to the study site (Department of Rheumatology) will be documented. Drug accountability will be documented with the description of the batch number, expiration date and date distributed to the subject. Patients are requested to keep a medication log which contains the day and time of the administration.

5. Procedures

5.1 Study procedures

A screening visit will include explanation and signing of the informed consent form and overview of in- and exclusion criteria in order to participate. If appropriate, a pregnancy test will be performed.

The maximum window allowed between the screening visit and the baseline visit is of 3 weeks.

Upon selection, patients will be included in the study during **the baseline visit**, which will include completion of NRS pain, a hand radiograph, Dual energy X-ray absorptiometry (DXA) and the laboratory investigations required. These will comprise a calcium and vitamin D status, kidney function tests (serum ureum, serum creatinine, GFR), bone turnover markers (BTM), and, if appropriate, a pregnancy test. A maximum of 45 ml of blood will be collected each visit.

Patients will be randomized to alendronate for 24 weeks or 48 weeks: study products (Steovess, alendronate 70mg every week) will then be provided to the patient. Calcium/Vit D supplementation will be installed.

Schedule of assessments are provided in detail as Appendix 1. Safety assessment is clarified in the safety paragraph.

At week 12: safety assessment NRS pain, BTM

At week 24: safety assessment, NRS pain, serum calcium levels and BTM, hand radiographs and DXA

At week 48: safety assessment, NRS pain, hand radiographs, DXA and the laboratory investigations required. These will comprise a calcium and vitamin D status, kidney function tests (serum ureum, serum creatinine, GFR), and BTM.

Safety: Patients will be able to report any unwanted effect during the regular visits and through telephone contact at any time in between these visits. Templates for AE/SAE recording created by the sponsor will be used.

A negative pregnancy test will be an entry requirement in female premenopausal patients. Premenopausal patients at risk to become pregnant will be excluded if no valid anti-conceptive method is used. In practice, premenopausal women will be an absolute minority in this study population. All through the time of the study pregnancy tests will be done during the visits.

	Distribution IMP	Safety	Laboratory ¹				CR hand	DXA	NRS pain	
			Kidney function	BTM	Vit D	Ca++	Preg. test*		L	
SCREENING / BASELINE	х	х	x	х	х	х	х	Х	х	х
WEEK 12 (+/- 7 days)	х	х		x			х			х
WEEK 24 (+/- 7 days)	х	х	x	x		х	х	х	х	х
WEEK 48 (+/- 7 days)		Х	x	x	Х	х	х	Х	х	х
						appr	* if opriate			

5.2 Study table

August 09 2019 - Version 1.0

Kidney function tests including serum creatinine, ureum and glomerular filtration rate (GFR). Depending on the individual patient, additional parameters may be added. ¹Samples must be obtained following an overnight fast during the morning.

5.3 Sample processing

Blood samples collected during the visits will be used for clinical analysis.

At baseline visit, W12, W24 and W48 three extra serum tubes will be collected. After centrifugation (4000 RT/10min) the serum will be allocated in vials of 1ml and stored at -80°C. At the end of the study those samples will be send to an external lab for analysis of the BTM.

6. Randomisation

The randomization code will be generated by a randomization manager. Randomization will be done in blocks of four.

7. Reporting requirements for investigational product complaints

The following could be considered potential product complaints that need to be reported to EffRx Pharmaceuticals. The Investigator will email the product complaint reports to [contact] and [contact]. Should any such concerns or irregularities occur, the IMP will not be used until confirms that it is permissible to use was received.

Examples of Product Complaints:

- Packaging: for example, broken container or cracked container
- Usage: for example, subject or healthcare provider cannot appropriately use the product
- Labeling: for example, missing labels, illegible labels, incorrect labels, and/or suspect labels
- Change in IMP appearance: for example color change or presence of foreign material
- Unexpected quantity in bottle: for example number of tablets or amount of fluid
- Evidence of tampering or stolen material

8. Concomitant therapy

In patients treated for osteoporosis symptomatic hypocalcemia has occurred, generally in association with predisposing conditions. Therefore, patients must be adequately supplemented with calcium and vitamin D levels during Steovess therapy. A calcium (1000 mg) and vitamin D (880 IU) supplement will be provided during the study visits as of the baseline visit. Daily intake following the approved dosage and regimen is requested. This supplement is considered to be an auxiliary medicinal products. Relabeling is not requested.

9. End of study

End of study is 30 days after the last visit at week 48 of last patient.

10.Adverse Events/Adverse Event reporting

The investigator will monitor each subject for clinical and laboratory (serum Ca⁺⁺ levels) evidence of adverse events on a routine basis throughout the study. The investigator will assess and record any adverse event in detail on the adverse event CRF including the date and time of onset, description, seriousness, severity, time course, duration and outcome, relationship of the adverse event to study drug, an alternate etiology for events not considered "probably related" to study drug, final diagnosis/syndrome (if known) and any action(s) taken. Adverse events, whether in response to a query, observed by study-site personnel, or reported spontaneously by the subject, will be recorded.

All adverse events will be followed to a satisfactory conclusion.

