3.1 Study design and schematic

This is a randomized study to investigate the effect of effervescent alendronate on BTM after denosumab discontinuation.

At the earliest three months but no later than four months after the last denosumab injection, 40 subjects will be randomized to effervescent alendronate administered for either 24 (n=20) or 48 weeks (n=20). The randomization code will be generated by a randomization manager. Randomization will be done in blocks of four.

Study schematic

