3.2 Number of sites

The study will be conducted in one site – the UZ Ghent site in Belgium.

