4.1. Composition and dosing

After denosumab discontinuation subjects will be randomized to receive open label effervescent alendronate (Steovess) for 24 or 48 weeks. Effervescent alendronate a bisphosphonate as effervescent tablets that should be taken once a week. Each effervescent tablet contains 70 mg alendronic acid as 91.37 mg of alendronate sodium trihydrate. Excipients are sodium dihydrogen citrate, citric acid anhydrous, sodium hydrogen carbonate, sodium carbonate anhydrous, strawberry flavour [Maltodextrin (Maize), arabic gum, propylene glycol (E 1520), nature-identical flavouringsubstances], acesulfame potassium and sucralose. Each tablet contains 602.54 mg of sodium. Effervescent alendronate is supplied as a white to off-white round effervescent tablets of 25 mm diameter, flat faced with bevelled edges.

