Annex I

IMP label

EudraCT N°: 2019-003570-11 TRIAL subject ID nr°: _____ Initialen: _____ Datum visite: _____ ENKEL VOOR STUDIEGEBRUIK Gebruiksaanwijzing: eenmaal per week een in leidingwater opgeloste bruistablet – 12 bruistabletten Elke bruistablet bevat 70mg alendronaat - Voor oraal gebruik - Buiten het zicht en bereik van kinderen houden – Bewaar in de originele verpakking ter bescherming tegen vocht. UNIQUEMENT POUR UTILISATION DE L'ESSAI CLINIQUE Mode d'emploi : un comprimé effervescent une fois par semaine, sous forme de solution buvable – 12 comprimés effervescents - Chaque comprimé contient d'alendronate 70mg - Voie orale - Tenir hors de la vue et de la portée des enfants - A conserver dans l'emballage extérieur d'origine, à l'abri de l'humidité. NUR STUDIENGEBRAUCH KLINISCHER Gebrauchsanweizung: Nehmen Sie einmal pro Woche eine in Leitungswasser gelöste Brausetablette ein. - 12 Brausetabletten - Jede Brausetablette enthält 70mg Alendronat - oraler Einnahme -Artznemittel für Kinder unzugänglich aufbewahren - In der Originalverpackung aufbewahren, um den Inhalt vor Feuchtigkeit zu schützen Exp:dayMONTHyear [name] [contact] SPONSOR: UZ GENT [name]

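### A single block size of four is stated for an open-label, single-site trial with no described concealment; deducible allocations could average anywhere from about 0 to 13.3 of 40, depending on when site staff learned the assigned duration

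*Protocol*

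**What the plan says.** Protocol section 3.1 describes the method in two sentences, "The randomization code will be generated by a randomization manager. Randomization will be done in blocks of four", and section 6 repeats them, again with "Randomization will be done in blocks of four". Forty subjects are split 20 and 20. Section 3.2 says "The study will be conducted in one site", and section 4.1 says "subjects will be randomized to receive open label effervescent alendronate (Steovess) for 24 or 48 weeks". Under section 5.1 patients are randomized at the baseline visit, and "study products (Steovess, alendronate 70mg every week) will then be provided to the patient". The visit table lists distribution of study drug at baseline, week 12 and week 24 without separating the arms. The label in Annex I is for twelve tablets: "12 bruistabletten Elke bruistablet bevat 70mg alendronaat".

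SAP section 2.3 adds that the randomization manager performed the randomization. The available text mentions no varied block sizes, envelopes, central system or rule for releasing an allocation. It also does not say when site staff or patients learned the assigned duration. The opening part of the SAP, apart from its table of contents, was not available for this check, and nothing is inferred from it.

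SAP section 4.1 makes the between-arm difference in CTX-I and P1NP at 48 weeks the primary endpoint. SAP section 5.2 analyses changes in the markers with a linear mixed model on all available time points and names no baseline covariate.

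**The concern.** At one site the same staff see the whole allocation sequence. If they know that blocks have four places, two per arm, and know all earlier allocations, the fourth allocation in every block is certain, and so is the third whenever the first two match. Someone who can foresee the next allocation could, even without intending to, bring a particular patient forward or hold one back.

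The comparison of 24 with 48 weeks depends on allocation being unpredictable. A difference between arms in the measured baseline marker can be adjusted for. Selection on traits that are not recorded, such as expected adherence, cannot. The other question, whether markers stay in range on alendronate overall, does not depend on the allocation.

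**Working it through.** The documents give no figure for predictability, so there is none to reproduce.

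**Inputs.** Block size 4, 1:1, 40 subjects (Protocol 3.1 and 6), so 10 blocks. A 2:2 split within each block is inferred from the ratio. Enrolment lasts 72 weeks (Protocol 3.3). Assumptions: an unstratified list, equally likely permutations, and staff who know the block size and where each block starts.

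**1. All earlier allocations known at enrolment.** Certain allocations in the six possible blocks:

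- AABB 2, BBAA 2
- ABAB 1, ABBA 1, BAAB 1, BABA 1

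Mean = (2 + 2 + 1 + 1 + 1 + 1)/6 = 8/6 = 1.33 of 4, or 33.3%.

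Over 10 blocks the count is 10 + Binomial(10, 1/3):

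- mean 10 + 10/3 = 13.3
- SD √(10 × 1/3 × 2/3) = 1.5
- P(11 to 16) = 0.963

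The logical limits are 10 and 20, with probabilities of 1.7% and 0.002%.

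Best guess at each position in turn: 1/2 + 2/3 + 2/3 + 1 = 17/6 of 4, or 70.8% correct, against 50% by chance.

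**2. Each allocation known only some weeks after entry.** Accrual is 40/72 = 0.556 per week, so a block fills in 4/0.556 = 7.2 weeks. Simulation with entry times uniform over 72 weeks (an assumption):

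| Delay (weeks) | Mean certain of 40 | Correct guesses |
|---|---|---|
| 0 | 13.3 | 71% |
| 1 | 8.7 | 65% |
| 3 | 3.5 | 58% |
| 6 | 0.8 | 52% |
| 12 | 0.03 | 50% |
| 24 | 0 | 50% |

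**3. Random blocks of 4 and 6, equal probability, full tracking.** Staff know the two possible sizes but not their order. Simulation with exact updating gives about 5.6% certain (2.3 of 40; 95% range 0 to 8) and about 69% correct guesses.

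Chance of 21:19 when stopping at 40: subjects 39 and 40 are equally likely, to a close approximation, to fall at each of five pairs of places (two in a block of 4, three in a block of 6). Three of those pairs leave a block unfinished, and the chance that the arms then differ by two is 1/3, 2/5 and 2/5. So (1/3 + 2/5 + 2/5)/5 = 0.227. Simulations of the same quantity gave 21% to 22%.

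**4. Baseline marker, a separate matter.** With 20 per arm the difference in baseline means has SD √(2/20) = 0.316 SD. P(|difference| > 0.5 SD) = P(|Z| > 0.5/0.316) = 0.114.

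Let r be the baseline to week 48 correlation, assumed 0.3 to 0.7, with equal SDs. If one arm starts 0.5 SD higher:

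- unadjusted change shifts down by 0.5 × (1 − r): 0.35 SD at r = 0.3, 0.15 SD at r = 0.7
- unadjusted week-48 level shifts up by 0.5 × r: 0.15 SD at r = 0.3, 0.35 SD at r = 0.7

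Both are shown because SAP 4.1 reads as a level and SAP 5.2 as a change.

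**The case against.** The strongest reply is that the full-tracking case is never established. Both arms take the same weekly tablet until week 24, and two packs of twelve would cover that period in either arm. Supplies could therefore look identical until then, and late disclosure would leave almost nothing to deduce. Randomization at the baseline visit suggests earlier disclosure but does not prove it. This objection stands, and it is why the result is a range.

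There was also little room to steer. A randomization manager held the code, and the pool was closed (Protocol 11.3). Entry had to fall in a one-month window, "At the earliest three months but no later than four months after the last denosumab injection", and the exclusions are explicit. Staff probably lacked the trial marker values when deciding on entry, since "At the end of the study those samples will be send to an external lab for analysis of the BTM", although section 5.1 does list bone turnover markers among the baseline tests. These points limit the concern without removing it, because none of them describes how the next allocation was hidden.

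Fixed blocks of four also guarantee 20:20, which is a defensible aim in a small closed pool. Varied blocks barely lower overall guessing, so timing of release matters more than block size. Both points are fair.

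Finally, the baseline covariate does not treat predictable allocation, and chance imbalance would arise under any randomization. That is correct, and it is offered here only as a separate SAP improvement. The mixed model may already include baseline as a response, since all available time points are used; SAP 5.2 does not say.

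**Conclusion.** The point holds as a minor design weakness. The protocol states a fixed block size of four, and the available text gives no concealment procedure for an open-label, single-site trial. Certain predictions average between about 0 of 40 (duration known to site staff 12 weeks or more after entry) and 13.3 of 40 (every earlier allocation known at enrolment). The documents do not place the trial within that range. The upper figure assumes that staff knew the block size and boundaries; the lower one assumes evenly spread accrual.

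A reader might infer that a third of allocations were known in advance, or as many as half, or that the comparison is biased. The documents support none of these. Nothing shows that earlier allocations were known at enrolment, one half is a logical limit with probability 0.002% even under full tracking, and no basis exists for a size of bias. Nor should the missing description be read as proof that allocation was unconcealed.

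The absence of a named baseline covariate in SAP 5.2 is a separate matter, with an 11% chance of a baseline gap above 0.5 SD. Such a gap would shift an unadjusted comparison by 0.15 to 0.35 SD, in a direction that depends on whether change or level is analysed.

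**What to change.** **Protocol, if amended or reused (sections 3.1 and 6).** Replace the fixed block of four with randomly varied small blocks, for example 4 and 6. Only the randomization manager should know the sizes, and each allocation should be released only after irrevocable registration. Under full tracking, certain predictions fall from 33% to about 6%, and correct guesses from 71% to 69%. The cost is a chance of roughly 22% of ending 21:19 instead of a certain 20:20. SAP section 6 foresaw the last visit in March 2022, so this is unlikely to help the present trial.

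**SAP section 5.2, separate and still usable.** Fit the mixed model to the week 12, 24 and 48 values of CTX-I and P1NP, with the baseline value of the same marker on the same scale as a covariate and not also as a response. Equivalently, keep baseline as a response and constrain the arms to a common baseline mean. If the analysis has already been run, report this result beside it and label it as added later. It costs one covariate that is already collected. It handles measured baseline imbalance only; it does not cure predictable allocation or selection on unrecorded traits.

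**Report.** A few sentences on who held the list, who knew the block size and when each allocation was released would show where in the range the trial fell.

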10.1. Definition

Adverse Event

An **adverse event** is defined as any untoward medical occurrence in a subject or clinical investigation subject administered a pharmaceutical product and which does not necessarily have a causal relationship with this treatment. An adverse event can therefore be any unfavorable and unintended sign (including an abnormal laboratory finding), symptom, or disease temporally associated with the use of a medicinal product, whether or not the event is considered causally related to the use of the product.

Such an event can result from use of the drug as stipulated in the protocol or labeling, as well as from accidental or intentional overdose, drug abuse, or drug withdrawal. Any worsening of a pre-existing condition or illness is considered an adverse event. Laboratory abnormalities and changes in vital signs are considered to be adverse events only if they result in permanent or temporary discontinuation of treatment with effervescent alendronate, necessitate therapeutic medical intervention and/or if the investigator considers them to be adverse events.

An elective surgery/procedure scheduled to occur during a study will not be considered an adverse event. However, if a pre-existing condition deteriorates unexpectedly during the trial (*e.g.*, surgery performed earlier than planned), then the deterioration of the condition for which the elective surgery/procedure is being done will be considered an adverse event.

Serious Adverse Event

If an adverse event meets any of the following criteria, it is to be considered as serious:

An event that results in the death of a subject.
An event that, in the opinion of the investigator, would
have resulted in immediate fatality if medical intervention
had not been taken. This does not include an event that

August 09 2019 - Version 1.0

would have been fatal if it had occurred in a more severe form.

Hospitalization An event that results in an admission to the hospital for any length of time. This does not include an emergency room visit or admission to an outpatient facility. **Prolongation of** An event that occurs while the study subject is hospitalized and prolongs the subject's hospital stay. Hospitalization **Congenital Anomaly** An anomaly detected at or after birth, or any anomaly that results in fetal loss. An event that results in a condition that substantially **Persistent or Significant** interferes with the activities of daily living of a study **Disability/Incapacity** subject. Disability is not intended to include experiences of relatively minor medical significance such as headache, nausea, vomiting, diarrhea, influenza, and accidental trauma (e.g., sprained ankle). An important medical event that may not be immediately **Important Medical Event** life-threatening or result in death or hospitalization, but **Requiring Medical or Surgical Intervention to** based on medical judgment may jeopardize the subject and may require medical or surgical intervention to prevent any **Prevent Serious Outcome** of the outcomes listed above (i.e., death of subject, lifethreatening, hospitalization, prolongation of hospitalization, congenital anomaly, or persistent or significant disability/incapacity). Examples of such events include allergic bronchospasm requiring intensive treatment in an emergency room or at home, blood dyscrasias or convulsions that do not result in inpatient hospitalization, or the development of drug dependency or drug abuse. **Spontaneous Abortion** Miscarriage experienced by study subject. **Elective Abortion** Elective abortion performed on study subject.

Adverse Event Severity

The investigator will use the following definitions to define/rate the severity of each adverse event:

Mild	The adverse event is transient and easily tolerated by the subject.
Moderate	The adverse event causes the subject discomfort and interrupts the subject's usual activities.

August 09 2019 – Version 1.0

Severe The adverse event causes considerable interference with the subject's usual activities and may be incapacitating or life-threatening.

Relationship to Study Drug

The investigator will use the following definitions to assess the relationship of the adverse event to the use of study drug:

- **Probably Related** An adverse event has a strong temporal relationship to study drug or recurs on re-challenge and another etiology is unlikely or significantly less likely.
- **Possibly Related** An adverse event has a strong temporal relationship to the study drug and an alternative etiology is equally or less likely compared to the potential relationship to study drug.
- Probably NotAn adverse event has little or no temporal relationship to the studyRelateddrug and/or a more likely alternative etiology exists.
- **Not Related** An adverse event is due to an underlying or concurrent illness or effect of another drug and is not related to the study drug (*e.g.*, has no temporal relationship to study drug or has a much more likely alternative etiology).

10.2. Adverse Event Reporting

Reporting will be consistent with current safety reporting standards. Adverse events will be reported between the first dose administration of trial medication and the last trial related activity.

All AEs and SAE's will be recorded in the patient's file and in the CRF. All SAE's will be reported as described below. A list of AEs considered possibly or probably related to Steovess/Binosto should be forwarded to EffRx at the end of the study at the latest.

Medical events that occur between signing of the Informed Consent and the first intake of trial medication will be documented on the medical and surgical history section and concomitant diseases page of the CRF.

SAE's occurring within a period of 30 days following the last intake of trial medication will also be handled as such if spontaneously reported to the investigator.

All serious adverse events (SAE) and pregnancies spanning from the first intake of IMP until the end of the study must be reported by the local Principal Investigator within 24h after becoming aware of the SAE to:

- The local EC
- Health, innovation and research institute (HIRUZ)
- The designated contact person of the Marketing Authorisation Holder (MAH) or producer of the medicinal (investigational) product

August 09 2019 – Version 1.0

This reporting is done by using the appropriate SAE form. For the contact details, see below. It is the responsibility of the local Principal Investigator to report the local SAE's to the local EC.

In case the investigator decides the SAE is a SUSAR (Suspected Unexpected Serious Adverse Reaction), HIRUZ will report the SUSAR to the Central EC and the CA within the timelines as defined in national legislation.

In case of a life-threatening SUSAR the entire reporting process must be completed within 7 calendar days. In case of a nonlife-threatening SUSAR the reporting process must completed within 15 calendar days.

The first report of a serious adverse event may be made by telephone, e-mail or facsimile (FAX).

Contact details of HIRUZ:

e-mail: [contact]

[contact]

[contact]

Contact details of producer: Pharmacovigilance department

e-mail: [contact] [contact]

The investigator must provide the minimal information: i.e. trial number, subject's initials and year of birth, medication code number, period of intake, nature of the adverse event and investigator's attribution.

A report of a serious adverse event by telephone must always be confirmed by a written, more detailed report. For this purpose the appropriate SAE form will be used. Pregnancies occurring during clinical trials are considered immediately reportable events. They must be reported as soon as possible using the same SAE form. The outcome of the pregnancy must also be reported.

As the subjects are not under 24-hour supervision of the investigator or his/her staff, they must be provided with a "trial card" indicating the name of the investigational product, the trial number, the investigator's name and a 24-hour emergency contact number.

Annual Safety and Progress Reporting

Hiruz CTU will ask the Chief Investigator for an annual report containing information on the status of the trial and an overview of all SSARs (Suspected Serious Adverse Reaction) and a summary regarding the safety of the trial subjects. Hiruz CTU will send this report to the Central EC and the CA within the timelines as defined in national legislation.

11.Statistical and Analytical Plans

